### 5.2. General Methods

*Continuous variables will be summarized by the N, mean, median, standard deviation, minimum and maximum. Categorical variables will be summarized by percent and counts. All summaries will be displayed by treatment group, and/or sequence, and/or period depending on the endpoint. Efficacy data will be listed, tabulated and graphically represented, as appropriate. Model assumptions will be tested using appropriate statistical or graphical techniques.*

All plots produced may be used as in-text plots in the CSR and therefore need to be optimized for inclusion, ie, legends, axis labels and titles should be clearly legible when inserted into one half of a page within the CSR.

To explore the data further and to assess the goodness-of-fit of all statistical models, separate SAS datasets will be provided by the clinical programmer to the statistician. Covariates for data exploration may include baseline and/or demographic covariates such as gender, age, weight (continuous and/or Pfizer standard categorical cut-offs), site, country, steroid usage, 4SC at baseline, etc.

*Change from baseline in functional assessments will be analyzed using a longitudinal mixed effects model, or mixed-effect model for repeated measures(MMRM). The baseline result, treatment, time and treatment by time interaction will be included as fixed effects in the model. The stratification factor of time to complete the 4 stair climb at baseline will be included in the model, see [Section 6.1.1](#), unless the baseline time to climb 4 stairs is included in the model. Subject will be included as a random effect and the model will be fit with an unstructured covariance for the repeated measures. If there are model convergence issues when using an unstructured covariance, then compound symmetry and autoregressive covariance structures will be explored to potentially address convergence issues and model fit. The distribution of the time to complete the functional assessment is assumed to be right skewed.*

*Transformations (including the log transformation) will be evaluated to ensure the normality assumption is met. Contrasts will be created to estimate the differences in change from baseline at the end of each dose treatment levels for Period 1 (Week 17, Week 33 and Week 49). The final analysis of the primary endpoint will be performed at Week 49, though data will continue to be collected through Week 97. Additionally, non-Gaussian models, such as Wilcoxon rank-sum test or Wei-Lachin test, may be explored in the case of non-normal data for the time to climb 4 stairs.*

Covariates will be summarized for the FAS and PPAS and by treatment. Continuous baseline covariates will be summarized by: n, mean, median, standard deviation, min and max. Binary and factor covariates will be summarized by percent and counts.

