#### 4.1. Inclusion Criteria

Subject eligibility should be reviewed and documented by an appropriate member of the investigator's study team before subjects are included in the study.

Subjects must meet all of the following inclusion criteria to be eligible for enrollment into the study:

1. Ambulatory boys age 6 to <16 years old (at the time of randomization), diagnosed with DMD. Diagnosis must be confirmed in subject's medical history and by genetic testing obtained during routine clinical care for diagnostic purposes as reported from an appropriate regulated laboratory using a clinically validated genetic test (genetic testing is not provided by the sponsor). Results must confirm the presence of a mutation in the dystrophin gene(s) which is clinically consistent with the diagnosis of DMD.
2. Subjects who are able to perform the 4 stair climb in  $\geq 0.33$  but  $\leq 1.6$  stairs/second at screening.\*
3. Evidence of a personally signed and dated informed consent and assent (where appropriate) document indicating that the subject and a legally acceptable representative/parent(s)/legal guardian have been informed of all pertinent aspects of the study.
4. Subjects and their legal guardians who are willing and able to comply with scheduled visits, treatment plan, laboratory tests, and other study procedures. Subjects will be required to provide assent in compliance with local regulations and IRB requirements.
5. Subjects must be receiving glucocorticosteroids for a minimum of 6 months prior to signing informed consent. There should be no significant change ( $>0.2$  mg/kg) in dosage or dose regimen (not related to body weight change) for at least 3 months immediately prior to signing the informed consent and a reasonable expectation that dosage and dosing regimen will not change significantly for the duration of the study.
6. Adequate hepatic and renal function on screening laboratory assessments:
  - $\text{GGT} \leq$  upper limit of normal (ULN).
  - Alkaline phosphatase  $\leq$  ULN.
  - Total Bilirubin  $\leq$  ULN.
  - Serum Albumin  $\geq$  LLN.
  - Serum creatinine  $\leq$  ULN.
7. No underlying disposition for iron accumulation on screening laboratory assessments:

- Serum Iron  $\leq 1.2 \times$  ULN.
  - Serum Ferritin  $\leq 140$  ng/mL.
  - % Transferrin Saturation  $\leq 50\%$ .
8. No underlying disposition for bleeding disorder on screening laboratory assessments:
- PT/INR  $\leq 1.25 \times$  ULN.
  - aPTT  $\leq 1.25 \times$  ULN.

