**6.6. Visits 6, 12, 18, 23, 27, 31 (Days 57, 169, 281, 393, 505, 617)**

This visit may be completed on the same day if logistics are permissive.

- **Fecal occult blood:** Fecal sample is to be collected at home within approximately 1 week prior to scheduled visit.
- **C-SSRS:** Children's Since Last Visit (Version 6/23/10).
- **PODCI Questionnaire.**

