#### **9.1. Sample Size Determination**

The sample size is based on the primary endpoint of demonstrating efficacy of change from baseline on a 4 stair climb timed function test as compared to placebo at 49 weeks. To detect a 2.5 second difference in change from baseline in 4 stair climb based on a difference between the active treatment and the placebo treatment in Period 1 assuming a common

standard deviation of 4.0 with 80% power at  $\alpha=0.05$  (two-sided), a 2:1 treatment allocation and one interim analysis a total of 96 subjects should complete 49 weeks of dosing for this assessment. Assuming a 10% attrition rate, approximately 105 subjects should be enrolled (70 subjects receiving PF-06252616 and 35 subjects receiving placebo) in order to ensure sufficient number of subjects will complete this assessment. If there are no safety issues and enrollment has completed, additional subjects may be enrolled prior to the time of the interim analysis. These additional subjects may help off-set any unforeseen variability that may occur outside the presumed standard deviation for this age group.

One interim analysis is planned to evaluate futility and efficacy after approximately 50% of the subjects have completed through Week 49. Alpha- and beta-spending functions will be used to determine the cutoffs for efficacy and futility at the interim based on the observed number of subjects in the interim analysis. The gamma family spending functions will be used to appropriately account for error spending and adjust for the observed information at the time of the interim analysis and conservative boundaries ( $\gamma \leq -1$ ) will be used to define the futility and efficacy boundaries. The cutoff used at the interim analysis will be calculated based on the percentage of subjects included at the interim analysis to ensure appropriate protection of the type I error. Further details regarding the interim analysis and simulations are included in the SAP.

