### **5.3. Methods to Manage Missing Data**

*Missing data will be handled using maximum likelihood techniques for a mixed effects model, also called a mixed-effect model for repeated measures(MMRM). This analysis is unbiased under the assumption of missing at random when the model assumptions hold. Subjects who lose the ability to complete a functional assessment and/or ambulate will be assumed to be missing not at random. Additional imputation methods to assess the sensitivity of the analysis to missing not at random data will also be performed. The methods include transforming time to complete a functional assessment to velocity, so that subjects with a missing time will be assumed to have a velocity of zero.*

Missing data for the PODCI patient reported outcome will be handled according to the guidance of the developers.

Values below the limit of quantification will be analyzed at the limit of quantification for that parameter except for PK data (see [Section 6.3.1.1](#)). For laboratory listings, the <BLQ will be used with the actual limit of quantification in place of BLQ.

For the primary endpoint analysis, ie, change from baseline to Week 49 on 4SC time, if there are >10% subjects who discontinue treatment before Week 49, then additional sensitivity analysis using ANCOVA model (or Wilcoxon test in case of rejection of normality of ANCOVA residuals) will be conducted and using the following two methods for handling the missing data:

- Jump-to-control with multiple imputation.
  - Assume subjects in active treatment group who discontinue treatment behave on average like control (placebo) group after discontinuation.
  - Implement using multiple imputation to get variability estimates.
- Tipping point analysis: In case the primary efficacy test using completers-only data is statistically significant, increase penalty for active treatment while having no penalty for placebo group, until the result is no longer statistically significant.

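### SAP 5.2 should name fallback covariance structures with visit-specific variances for the primary 4SC model; an equal-variance fallback could put two-sided Week 49 error at about 6.2% to 7.7%

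*SAP*

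**What the plan says.** SAP 6.1.1 analyses change in 4SC time with the model of SAP 5.2, using data through Week 49. On the covariance, SAP 5.2 says "Subject will be included as a random effect and the model will be fit with an unstructured covariance for the repeated measures". Protocol 9.2.1 and the protocol summary carry the same sentence. SAP 5.2 and 5.3 also label the model an MMRM.

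The SAP has one provision for convergence trouble with the unstructured fit: "then compound symmetry and autoregressive covariance structures will be explored to potentially address convergence issues and model fit". The protocol names no fallback. Neither document says which structure would carry the primary test, in what order they would be tried, whether variances may differ by visit, or whether robust standard errors would be used.

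Two general provisions bear on this. SAP 5.2 states "Model assumptions will be tested using appropriate statistical or graphical techniques", and also "Transformations (including the log transformation) will be evaluated to ensure the normality assumption is met". Neither says what follows for the covariance if equal variances look wrong.

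**The concern.** The Week 49 contrast is the primary test. An unstructured covariance gives Week 49 its own variance. Compound symmetry (CS) and first-order autoregression (AR(1)), in their standard forms, pool one variance over all visits. In a progressive disease the spread of change from baseline may well be smaller at Week 9 than at Week 49. Pooling would then bring the smaller early variances into the Week 49 standard error, and the test would reject too often under the null. Because the fallback is only to be explored, the choice of primary test would be made after the fit has failed, with no rule to settle it.

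**Working it through.** **Inputs**
- Planning SD of change: Protocol 9.1, "standard deviation of 4.0 with 80% power". Neither document gives an SD for any visit before Week 49.
- 4SC visits after baseline in Period 1: Weeks 9, 25 and 41 (Protocol 6.6) and Weeks 17, 33 and 49 (Protocol 6.8), so six. The SAP's named contrasts are Weeks 17, 33 and 49 only, so a three-visit model is also computed.
- Assumed: Week 9 SD equal to k times the Week 49 SD, with k = 1.0, 0.9 or 0.8, and SD linear over visits. The results depend on k, not on the level of the SD.

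**1. The plan's own figure.** N = (1.96 + 0.8416)² × 4.0²/2.5² × (3 + 1.5) = 90.4, or 93 when rounded to 2:1. Gamma spending with -2 for both boundaries at 50% information (my choice within the stated limit of -1 or below; non-binding futility) multiplies 90.4 by 1.063, giving 96.1. This agrees with the stated 96 completers. At 64 versus 32, the true Week 49 standard error is 4.0 × √(1/64 + 1/32) = 0.866 s.

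**2. Equal-variance fallback, large sample.** With complete data, CS replaces the Week 49 variance by the mean variance over visits:

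R = √(mean of SD²) / SD at Week 49; two-sided error = 2 × [1 - Φ(1.96 × R)].

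| k | Visits | Mean variance | R | 1.96 × R | Error |
|---|---|---|---|---|---|
| 1.0 | 6 or 3 | 16.00 | 1.000 | 1.960 | 5.0% |
| 0.9 | 6 | 86.752/6 = 14.46 | 0.951 | 1.863 | 6.2% |
| 0.8 | 6 | 78.208/6 = 13.03 | 0.903 | 1.769 | 7.7% |
| 0.9 | 3 | 44.288/3 = 14.76 | 0.961 | 1.883 | 6.0% |
| 0.8 | 3 | 40.832/3 = 13.61 | 0.922 | 1.808 | 7.1% |

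For k = 0.8 the six SDs are 3.20, 3.36, 3.52, 3.68, 3.84 and 4.00 s. One-sided, six-visit error is 3.1% (k = 0.9) or 3.8% (k = 0.8) against 2.5%. For AR(1), minimising log|V| + tr(V⁻¹Σ) gives 6.2% and 7.6% to 7.7%. All figures treat the test as a single look.

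**3. Simulation.** 3,000 null trials per ratio, 70 versus 35 boys, six visits, 10% monotone dropout, REML, baseline covariate, true correlation AR(1) at 0.8. The Monte Carlo standard error is about 0.4 points at 5%. Two-sided rejection:

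| k | Unstructured | CS | AR(1) | Either CS or AR(1) | Het. Toeplitz | Het. AR(1) | Het. CS |
|---|---|---|---|---|---|---|---|
| 1.0 | 4.6% | 4.7% | 4.5% | 5.1% | 4.6% | 4.6% | 4.2% |
| 0.9 | 4.7% | 6.3% | 5.9% | 6.9% | 4.6% | 4.6% | 4.0% |
| 0.8 | 5.5% | 8.5% | 8.4% | 9.2% | 5.4% | 5.2% | 4.3% |

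The mean CS standard error was 0.81 s (k = 0.9) and 0.77 s (k = 0.8), against a true 0.88 s. Taking whichever of CS or AR(1) is significant adds 0.4 to 0.7 points over CS alone, so the unstated order matters little. The heterogeneous forms stay at 4.0% to 5.4%.

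**4. How often the fallback is reached.** Without the random effect, the unstructured model converged in all 12,000 simulated trials (3,000 at each of four ratios, three shown).

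**5. The random subject effect.** Six visits give 6 × 7/2 = 21 covariance elements. A subject variance makes 22 parameters, and the map to the 21 elements has rank 21, so that variance is not identifiable. In 900 literal 22-parameter fits, all converged, and the Week 49 estimate and standard error matched the unstructured fit within 0.00001 s. Commercial software was not tested.

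**The case against.** The strongest objection is that the fallback may never be used. Nothing in the simulations triggered it, so every error figure is conditional on an event not observed there. That stands, with two limits: the simulated data were well behaved, and SAP 6.2 and 6.4 apply the same methods within baseline 4SC subsets, where fewer boys must support the same covariance. No simulation was run for those.

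Second, the SAP does not say that variances are equal; heterogeneous forms may have been meant. That is fair. If so, saying so closes the point.

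Third, SAP 5.2 mentions model fit as a purpose and provides for goodness-of-fit checks. A large-sample likelihood-ratio test of equal against visit-specific variances (96 boys, six visits) has power of roughly 50% to 83% at k = 0.8 but only 13% to 33% at k = 0.9. Such a check might reveal the problem, but the SAP attaches no consequence to it. The Week 49 ANCOVA or Wilcoxon analyses (SAP 5.3) and the rank-sum test (SAP 6.1.2) do not pool variance over visits, but they are conditional sensitivity analyses and do not replace the primary test.

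Fourth, the calculations are in seconds. A log scale could bring the error near nominal; this was not calculated.

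A reader might infer that the random effect makes the primary model unfittable or biases its result. The documents do not support that: the MMRM label allows subject to mean only the repeated-measures cluster, and the literal fit leaves the Week 49 result unchanged. A reader might also infer much larger inflation from a steeper rise in SD. No document gives an SD by visit to support that, and a steep rise would very probably show in a fit check.

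**Conclusion.** The point holds as a minor, conditional weakness. The only fallbacks the SAP names are, in standard form, equal-variance structures, and no rule says which becomes the primary test. Two-sided Week 49 error would be about 6.2% to 7.7% with six visits, or 6.0% to 7.1% with three, for assumed Week 9 to Week 49 SD ratios of 0.9 to 0.8. It is 5.0% if the SD is constant.

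This needs four things together: the fallback is reached, an equal-variance form is used, its model-based standard error carries the primary test, and spread grows on the scale analysed. The sample size is unaffected. The redundant random effect is a wording matter, though some software may flag it as a fitting problem and so trigger the fallback needlessly.

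**What to change.** In SAP 5.2, keep the unstructured covariance and replace the fallback wording with, for example: *If the unstructured model does not converge, the primary test will use the first of these that converges: heterogeneous Toeplitz, heterogeneous AR(1), heterogeneous compound symmetry.* The exact order matters little; what counts is that it is fixed before unblinding and that each structure allows visit-specific variances.

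As a tidy-up, delete the random-subject sentence or state that subject only identifies the repeated-measures cluster. This also settles the fallback models, since a random intercept with AR(1) is an identified model different from AR(1) alone.

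The cost is one or two SAP sentences. Protocol 9.2.1 and the protocol summary can be aligned on the random effect at the next amendment; they have no fallback text to change. With six visits, the three structures use 11, 7 and 7 covariance parameters instead of 2, and heterogeneous compound symmetry was slightly conservative in simulation (4.0% to 4.3%). Sample size, data collection and conduct do not change.

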### **5.3. Methods to Manage Missing Data**

*Missing data will be handled using maximum likelihood techniques for a mixed effects model, also called a mixed-effect model for repeated measures(MMRM). This analysis is unbiased under the assumption of missing at random when the model assumptions hold. Subjects who lose the ability to complete a functional assessment and/or ambulate will be assumed to be missing not at random. Additional imputation methods to assess the sensitivity of the analysis to missing not at random data will also be performed. The methods include transforming time to complete a functional assessment to velocity, so that subjects with a missing time will be assumed to have a velocity of zero.*

Missing data for the PODCI patient reported outcome will be handled according to the guidance of the developers.

Values below the limit of quantification will be analyzed at the limit of quantification for that parameter except for PK data (see [Section 6.3.1.1](#)). For laboratory listings, the <BLQ will be used with the actual limit of quantification in place of BLQ.

For the primary endpoint analysis, ie, change from baseline to Week 49 on 4SC time, if there are >10% subjects who discontinue treatment before Week 49, then additional sensitivity analysis using ANCOVA model (or Wilcoxon test in case of rejection of normality of ANCOVA residuals) will be conducted and using the following two methods for handling the missing data:

- Jump-to-control with multiple imputation.
  - Assume subjects in active treatment group who discontinue treatment behave on average like control (placebo) group after discontinuation.
  - Implement using multiple imputation to get variability estimates.
- Tipping point analysis: In case the primary efficacy test using completers-only data is statistically significant, increase penalty for active treatment while having no penalty for placebo group, until the result is no longer statistically significant.

## 6. ANALYSES AND SUMMARIES

### 6.1. Primary Endpoint

#### 6.1.1. Primary Analysis

The primary endpoint, change from baseline in 4 stair climb, will be analyzed based on the FAS using the mixed effects model outlined in [Section 5.2](#). For primary efficacy analysis, besides FAS, PPAS will be used to assess the sensitivity of the analysis results. These analyses will be performed based on the data for all subjects through 49 weeks. Subjects in sequence 1 and 2 will be combined for analysis purposes and compared to the placebo subjects in sequence 3. Covariates for this analysis include the time to climb 4 stairs at baseline, treatment, visit and treatment by visit interaction. Model estimates and change from placebo estimates, 95% two-sided confidence intervals, and p-values will be displayed for study interpretation purposes. Model estimates with confidence intervals will also be displayed graphically. Graphical summaries of the raw data, including boxplots, will be created to highlight outliers and other influential observations.

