### **4.3. Randomization Criteria**

Subjects will be randomized into the study provided they have satisfied all subject selection criteria. During the randomization, the results of the 4 SC from the baseline visit will be provided for stratification. Subjects will be stratified into two groups, those completing the 4 stair climb in  $\leq 8$  seconds and those completing in  $> 8$  seconds. Results from the *screening* 4 SC (not the baseline 4SC) will be used to determine subject's eligibility. The baseline 4SC will be used for all analysis.

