### **6.2.1. Historical Control**

*In keeping with global guidance (eg, Food and Drug Administration’s Guidance from 2015: Duchenne Muscular Dystrophy and Related Dystrophinopathies: Developing Drugs for Treatment and European Medicinal Agency[EMA]/Committee for Medicinal Product for Human Use [CHMP] Guideline on the Clinical Investigation of Medicinal Products for the Treatment of Duchenne and Becker muscular dystrophy, 2016) and related advice received from regulators, the long-term effects on functional assessments following approximately 2-years of treatment with PF-06252616 will be characterized compared to a historical control. This historical control group will be established by filtering available natural history datasets (eg, CINRG dataset) to match covariates including but not limited to baseline 4SC time range, baseline age interval, and the baseline glucocorticosteroids requirements defined by the protocol.*

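### The primary MMRM adjusts only for baseline 4SC; pre-specifying age with an age-by-visit term could recover a modest amount of precision at almost no cost

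*SAP*

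**What the plan says.** SAP 6.1.1 lists the terms of the primary model: "Covariates for this analysis include the time to climb 4 stairs at baseline, treatment, visit and treatment by visit interaction". SAP 5.2 and Protocol 9.2.1 give the same fixed effects. SAP 3.4 takes the baseline from the baseline visit, and Protocol 4.3 separates that reading from the screening reading, which decides eligibility: "The baseline 4SC will be used for all analysis".

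Age is available for every boy, since Protocol 6.1.1 collects date of birth. The range is wide: "Ambulatory boys age 6 to <16 years old (at the time of randomization), diagnosed with DMD" (Protocol 4.1). Elsewhere age appears in these places:

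- SAP 5.2, as an option for exploration: "Covariates for data exploration may include baseline and/or demographic covariates such as gender, age, weight".
- SAP 6.2, as an optional covariate for the thigh-volume endpoints to allow for growth, and where appropriate in the regressions of 4SC on MRI.
- SAP 6.2.1, as a matching factor for the historical control: "including but not limited to baseline 4SC time range, baseline age interval".
- Protocol 1.3, in the natural history, which places most loss of walking at 10 to 14 years.

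SAP 3.4 also allows further covariates to be tried in the 4SC model. Neither the primary model nor any named sensitivity analysis includes age.

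**The concern.** When a covariate predicts the outcome beyond what the model already contains, leaving it out keeps its share of the variance in the residual. The Week 49 comparison is then less precise than the collected data would allow. Age is a plausible candidate. The eligible range spans the years in which the Protocol says most boys stop walking, and the historical comparison matches on age as well as on baseline 4SC, so baseline 4SC alone was not thought sufficient there. Randomisation is stratified on baseline 4SC only.

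Timing also matters. An age adjustment chosen after unblinding would carry little weight, while one fixed in advance is an ordinary part of the model. A smaller benefit concerns missing data: the primary analysis assumes missing at random, and conditioning on a variable linked to loss of ambulation makes that a little more plausible. It does not resolve the missing-not-at-random cases that the plan itself acknowledges.

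**Working it through.** **Inputs.** Protocol 9.1 gives the effect ("To detect a 2.5 second difference in change from baseline in 4 stair climb"), the spread and power ("standard deviation of 4.0 with 80% power"), two-sided α = 0.05, 2:1 allocation, one interim analysis and 96 completers. The interim is at about 50%, with gamma-family spending and γ ≤ −1. The exact γ is not visible, so γ = −1 is assumed here for efficacy, with futility treated as non-binding. Protocol 9.1 does not say whether the SD of 4.0 s is raw or baseline-adjusted; it is taken as the residual SD.

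**Step 1: reproduce the plan's figure.**

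- Fixed design, 2:1: N = 4.5 × [SD × (1.960 + 0.842)/δ]² = 4.5 × (4.0 × 2.8016/2.5)² = 90.4.
- Interim α (one-sided): 0.025 × (1 − e^0.5)/(1 − e^1) = 0.00944. The bounds are z = 2.348 and 2.066, and the sample-size inflation is 1.052.
- 90.4 × 1.052 = 95.1, rounded to 32 + 64 = 96. This matches the Protocol. Power at 96 is 80.4%.

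γ = −2 for both efficacy and binding futility also gives about 96, so the match does not identify γ.

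**Step 2: effect of an extra covariate.** Let R² be the share of Week 49 residual variance that age explains beyond baseline 4SC. The documents give no value, so a range is shown. SE = 4.0 × √(1 − R²) × √(1/32 + 1/64); completers for 80% power = 95.1 × (1 − R²).

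| Assumed R² | SD (s) | SE (s) | Power at 96 | Completers for 80% |
|---|---|---|---|---|
| 0 | 4.00 | 0.866 | 80.4% | 95 |
| 0.01 | 3.98 | 0.862 | 80.8% | 94 |
| 0.02 | 3.96 | 0.857 | 81.2% | 93 |
| 0.03 | 3.94 | 0.853 | 81.6% | 92 |
| 0.05 | 3.90 | 0.844 | 82.4% | 90 |
| 0.10 | 3.79 | 0.822 | 84.4% | 86 |

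**Step 3: what the adjustment costs.** Period 1 has six post-baseline 4SC visits (Weeks 9, 17, 25, 33, 41 and 49), so age plus age-by-visit adds up to six coefficients. The Week 49 contrast pays for roughly one of them. Estimating one slope inflates its variance by about 1/(96 − 1 − 3) = 1.1%. The break-even R² is therefore about 1%, and the gain is immaterial below about 1–2%.

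**Step 4: one age coefficient, or one per visit?** Suppose the age effect on change grows in proportion to time, d_v = d_49 × (week − 1)/48, with age in SD units. A single common coefficient is then b = (1′Σ⁻¹d)/(1′Σ⁻¹1), and the Week 49 variance becomes σ² + (d_49 − b)². The early visits are less variable and pull b towards their small effects. Take a Week 49 SD of 4.0 s, measurement noise of 0.5–2 s, and random-slope or Brownian residuals (all assumptions). A common coefficient keeps only about 0.1–1.7 percentage points of an assumed 3% reduction, and from 0.4 to a little under 6 points of an assumed 10%. The age-by-visit term keeps all of it.

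**The case against.** The case for leaving the model alone is respectable. For 4SC decline, the plan's chosen predictor is baseline 4SC. It defines the strata and the subsets, and it is in the model. Age overlaps with it, so what age adds may be small. The evidence that age is prognostic for 4SC is indirect: the MRI models allow age because of growth, and the historical control is matched because that comparison is not randomised. Every figure for the gain is assumed. All of this stands, and it limits the point to a modest one. It does not remove it, because the Protocol itself ties loss of walking to age within the eligible range, and the adjustment uses data already held.

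The permission in SAP 3.4 to explore covariates is only a partial answer, because exploration after the fact does not fix the primary test.

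A reader might infer three stronger things that the documents do not support.

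- That the primary analysis is biased, or the trial mis-sized. Randomisation and the reported confidence interval already cover chance age imbalance, and 96 reproduces.
- That the screening 4SC should be added as a second baseline reading. Eligibility is truncated on it, it can precede baseline by weeks, it may be repeated or come from a re-screen, and Protocol 4.3 sets it apart from the analysis. Its likely contribution, on assumed reliabilities of 0.80–0.95, is mostly 1–4% of variance before allowing for that truncation.
- That a single age coefficient would deliver the whole gain. Step 4 of the working shows that it would not if the age effect grows over time.

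**Conclusion.** The point holds as a modest efficiency improvement. The primary model omits a baseline variable that is collected, spans a wide range and is treated as prognostic elsewhere in the documents. With an age-by-visit term and an assumed extra 3–10% of Week 49 residual variance explained, power at 96 completers goes from about 80% to about 82–84%. Put differently, about 92 to 86 completers would give 80% power in place of 95. The cost of estimating the slope takes back roughly half a percentage point of that power.

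This rests on an assumed R², on 4.0 s being the residual SD, and on γ = −1. The documents supply no correlation from which the gain could be derived, and it could be negligible. Nothing here calls into question the validity of the planned analysis, its type I error or the sample size.

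**What to change.** Before unblinding, amend SAP 6.1.1, the matching text in SAP 5.2 and Protocol 9.2.1 (repeated in the Protocol Summary). The primary MMRM would then have these fixed effects: baseline 4SC, age at randomisation, treatment, visit, treatment-by-visit and age-by-visit. State the form of age in advance, for example linear in years. Use the same terms in the velocity sensitivity analysis of SAP 6.1.2. Keep the baseline-visit 4SC as the only 4SC covariate and leave Protocol 4.3 as it is. Protocol 9.4 requires the interim plan to be approved before the independent team is unblinded, so the change should be settled by then and the interim 4SC test should use the same model.

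Cost: up to six coefficients in the model (about one for the Week 49 contrast), with no new data or visits. SAP and Protocol wording must change, and Protocol 9 and SAP 2 call for a protocol amendment if this counts as a major modification of the primary analysis.
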